The study will address the following objectives: (1) demonstrate the feasibility of our study procedures including patient recruitment, screening and outcome measures, and feasibility of adapting our intervention bundle and its intervention delivery process within three older surgical patient populations (i.e., orthopedic, oncologic, and cardiac); (2) empirically test the effectiveness of our adapted perioperative mental health intervention bundle with clinically significant symptoms of depression and/or anxiety; and lastly (3) identify implementation strategies to ensure acceptability, feasibility, and adoption of our intervention bundle by patient and clinician stakeholders. Insights gained from this pilot study will inform the design of three clinical trials that are planned to start in Jan 2023. This project is led by research team members of the newly established Center for Perioperative Mental Health <https://perioperativewellness.wustl.edu/> that strives to improve perioperative mental health and well-being for older adults.

3 Study Setting and Participants

The study will be conducted at Barnes-Jewish Hospital and Washington University School of Medicine locations, including Siteman Cancer Center and Barnes-Jewish West County Hospital. Participants will include patients and caregivers. We expect to recruit and enroll up to 70 participants total in this study: up to 45 patients, up to 12-15 in each of 3 surgical cohorts; up to 25 caregiver participants.

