3.1 Patient Participants

3.1.1 Inclusion criteria

Patients will be included if they meet **all** of the following eligibility criteria:

1. Age ≥ 60 years on the day of surgery;
2. Scheduled major orthopedic surgery, or major surgical resection of a thoracic or abdominal malignancy, or major cardiac procedure;
3. Clinically significant depression or anxiety symptoms screened by the PHQ-ADS (Patient Health Questionnaire Anxiety and Depression Scale) ≥ 10 [7].

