3.4.2 Caregiver consent

Caregivers will be invited to participate in semi-structured interviews about the intervention bundle that can be conducted via Zoom/Phone or in-person depending on participant convenience and choice. Hence, they will be consented verbally or with a written consent depending on their participation. If they consent to a semi-structured interview (Appendix J). The interviews with study patient caregivers, will provide valuable feedback on the intervention bundle. Caregivers may also consent verbally to participate in the FAM-CAM confusion and delirium assessment via phone, mail, or email link to REDCap survey.

4 Study Design

This is a feasibility study utilizing mixed methods. All eligible and consenting patients will receive the intervention bundle and will undergo a standard battery of assessments prior to the intervention and will be followed for approximately 3 months in the postoperative period. In conjunction with the

quantitative data collected, qualitative methods will be employed to evaluate acceptability, implementation and practicality of the intervention.

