4.2 Perioperative Mental Health Intervention Bundle

Our intervention bundle will be initiated prior to surgery and continue postoperatively, and will span for approximately 3 to 4 months across the perioperative period (including pre- and 3 month post-operative periods). The personalized intervention bundle is comprised of behavioral activation and medication optimization, both facilitated by specially trained interventionists on the research team.

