4.3.2.1 Potential Study Primary Outcomes for Planned RCT

Effectiveness outcomes will include the primary outcome measure of PHQ-ADS, a validated composite scale of depression and anxiety symptoms [7] measured at baseline, 1, and 3 months after surgery. The Behavioral Activation for Depression Scale, or BADS (activation subscale), is our primary measure of target engagement. BADS is a sensitive and pragmatic assessment of the mechanism of change in Behavioral Activation. Approximately three months post-operative is the primary endpoint.

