The quantitative data will be used to provide baseline and post-intervention comparisons on a number of outcome variables relevant to the intervention, with the hypothesis that performance on these measures will improve post intervention. These data will also be used to estimate effect sizes for further trials so that these are suitably powered. Quantitative data will be tabulated for descriptive purposes. Given the small sample size, a non-parametric approach will be used to calculate effect size data ($r = Z/\sqrt{N}$), where Z is the standardized test-statistic from a Wilcoxon signed-rank test and N is the sample size, along with the associated 95% confidence interval. The r values will be calculated for the timepoint as compared to baseline.

The observation data will be analyzed using open coding and FRAME analytic framework that helps track any adaptations to intervention bundle and delivery. The interview data will be analyzed using thematic analysis [8].

Table 3. Study Calendar

	Time 0	Baseline/ Time 1	In- Hospital / Post-Op	1 mo follow up	2 mo follow up	3 mo follow up	Post- EOS
Patient Consent	X						
Patient Screening (Appendix A)	X						
Patient Baseline surveys (Appendix D)		X					
Caregiver Consent		X					X
Patient Delirium Assessment (Appendix K) pt UB/ 3-D CAM ; & Caregiver if applicable, FAM-CAM		X (pt)	X(pt) twice daily x 3	FAM- CAM if applicable			

1x weekly for 4 weeks.			days post-op	(weekly x 4wks)			
Patient Follow-up 1 & 3 mo Surveys (Appendix G)				X		X	
Patient Monthly Surveys (Appendix L)				X	X	X	
Patient Post-EOS Surveys (Appendix I)							X*
Patient Semi-Structured Interview (Appendix J)							X*
Caregiver Semi-Structured Interview (Appendix J)							X*
Behavioral Activation and Medication Review Intervention Sessions				Approximately 6-12 sessions as needed (per Pt preference) from Baseline, continuing for up to approximately 3 months post-op during study data collection, until EOS.			

*Post-End of Study (EOS) implementation surveys and semi-structured interviews will be completed approximately 2 weeks after EOS assessment.

6 Patient Participant Retention

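### Objective 2 promises a test of effectiveness, but a single treated group compared before and after major surgery cannot separate the bundle from surgery, recovery and time

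*Combined protocol and SAP*

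**What the plan says.** The objectives paragraph, just before Section 3, lists three numbered aims. The second is to "empirically test the effectiveness of our adapted perioperative mental health intervention bundle" in patients with clinically significant depression or anxiety symptoms.

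The design behind that aim is as follows.

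- **Allocation.** Section 4: "All eligible and consenting patients will receive the intervention bundle". No control arm, historical comparator or benchmark is described anywhere.
- **Event between the measurements.** Section 3.1.1 requires "Scheduled major orthopedic surgery, or major surgical resection of a thoracic or abdominal malignancy, or major cardiac procedure".
- **Timing of treatment.** Section 4.2: "Our intervention bundle will be initiated prior to surgery and continue postoperatively", to about 3 months after the operation.
- **Timing of measurement.** Section 4.3.2.1 has PHQ-ADS "measured at baseline, 1, and 3 months after surgery". Section 4.1 takes the screening score as the baseline value. Table 2.1 has VR-12 at baseline, 1 and 3 months, and BADS at baseline, 1, 2 and 3 months.
- **Analysis.** Section 5 compares baseline with post-intervention values "with the hypothesis that performance on these measures will improve post intervention". The statistic is r = Z/√N from a Wilcoxon signed-rank test, with a 95% confidence interval: "The r values will be calculated for the timepoint as compared to baseline".

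Section 5 puts no limit on what may be concluded from that comparison. Table 2, the study's own outcome list, contains reach, data completeness and implementation potential. PHQ-ADS appears there only as completeness of collection.

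**The concern.** A test of effectiveness needs some estimate of what would have happened without the bundle, and this design has none. Baseline falls before a major operation and the last follow-up about 3 months after it, while the bundle runs across the same interval. Surgery, recovery, relief of pre-operative worry and the bundle are therefore completely overlapped. The same applies to BADS and VR-12, because activity and function can move with the operation itself.

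At stake is the conclusion that may be drawn. A bundle that does nothing could satisfy the Section 5 hypothesis. A bundle that works could fail it if pain, complications or the course of a malignancy push symptoms up. Either result could be reported as the answer to Objective 2 and carried into the three trials this pilot is meant to inform.

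**Working it through.** **Figures available.** The plan states no power, significance level, sidedness, SD of change or expected course without the bundle, so there is no planned figure to reproduce. The enrolment arithmetic agrees: 3 × 15 = 45 patients, and 45 + 25 caregivers = 70.

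**Why the effect is not identified.** Let B be the bundle effect and S the change the same patients would have shown with surgery and time but no bundle. The study observes D = B + S, which is one equation in two unknowns. A mean fall of 3 points fits B = −3 with S = 0, and equally B = 0 with S = −3. A mean change of zero fits B = −3 with S = +3. More patients sharpen D but do nothing to split it.

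**Illustration of size.** Assumed inputs, none from the documents except the enrolment ceiling of 45:

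- true bundle effect zero;
- 45 complete pairs;
- SD of PHQ-ADS change σ = 6 to 10;
- natural fall δ from −2 (worsening) to 4 points;
- significance taken as Z > 1.96 in the improving direction (one-sided 2.5%). At N = 45 this is r above 1.96/√45 = 0.29.

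A large-sample approximation for the signed-rank test is P ≈ Φ[(δ/σ)·√(3n/π) − 1.96]. For n = 45, √(3 × 45/π) = 6.555. With δ = 3 and σ = 8, this gives 0.375 × 6.555 − 1.96 = 0.498, so P ≈ 69%. Simulating the signed-rank test on rounded normal changes gives 67%; the formula runs slightly high.

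| Natural change in PHQ-ADS | Formula, SD 8 | Simulated, SD 10 to SD 6 |
|---|---|---|
| worsens by 2 | <0.1% | about 0% |
| none | 2.5% | 2-3% |
| falls by 1 | 13% | 9-18% |
| falls by 2 | 37% | 25-56% |
| falls by 3 | 69% | 46-90% |
| falls by 4 | 91% | 72-99% |

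Forty-five is a ceiling. At SD 8 and a 3-point fall, the formula gives 0.375 × 5.863 − 1.96 = 0.239, or 59%, for 36 pairs (simulated about 58%). For 30 pairs it gives 0.375 × 5.352 − 1.96 = 0.047, or 52% (simulated about 47-50%).

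Simulation error is one or two percentage points. The table leaves out any fall due to regression to the mean from using the screening score (entry at 10 or more) as baseline. That is a separate matter.

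**The case against.** The strongest reply is that the protocol already defers effectiveness. Section 4 calls this a feasibility study, the primary outcomes in Section 4.3.1 are reach, and the secondary outcome is completeness. PHQ-ADS and BADS sit under a heading for potential outcomes of the planned RCT. The sentence "Approximately three months post-operative is the primary endpoint" comes from that section, so it need not be read as a designated efficacy endpoint of this study. All of that stands, and it limits the harm to Objective 2 and the Section 5 hypothesis. It does not remove the problem: the numbered objective still promises a test, Section 5 still supplies a directional hypothesis and a statistic, and neither carries a caveat. Table 2 makes the mismatch plainer, since Objective 2 has no effectiveness outcome there.

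A second reply is that Section 5 sets no significance level or success rule, so the 2.5% benchmark is not the plan's. That is correct. A signed-rank test that detects a real 3-point fall has answered its own question properly; the error would be in attributing the fall to the bundle. The percentages show how easily the hypothesis could be met without any bundle effect. They are not an error rate of the plan.

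A reader might go further and infer that the comparison is bound to credit the bundle with ordinary recovery. The documents do not support that. They give no natural-course data, and pain, complications or disease course could equally hide a benefit.

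**Conclusion.** Objective 2, as worded, claims something the design cannot deliver. This follows from the structure alone: everyone is treated, everyone has major surgery in the interval, and the only comparison is with the patient's own baseline. It needs no numerical assumption.

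The direction and size of any bias are unknown. Under the assumptions above, the chance that an ineffective bundle shows a significant improvement runs from about 0% to 99%, depending almost wholly on the unmeasured natural course. No single entry should be read as the expected value; the 67% at SD 8 depends on the chosen 3-point fall and on 45 complete pairs.

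This should be fixed, but it is not grounds for holding the study. A reader might infer that the pilot as a whole is unsound. It is not: reach, data completeness and implementation potential do not depend on the before-after comparison.

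**What to change.** 1. Reword Objective 2 along these lines: *describe the within-patient change in PHQ-ADS, BADS and VR-12 from baseline to each scheduled follow-up, with its variability*. Naming each scheduled follow-up covers the 2-month BADS assessment in Table 2.1.
2. In Section 5, replace the improvement hypothesis with the same descriptive aim. Add a sentence that no conclusion on effectiveness will be drawn, because surgery and time are not separated from the bundle.

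This also brings Objective 2 into line with Table 2. Reporting the depression and anxiety parts of PHQ-ADS separately is optional; it may be informative but does not separate surgery from bundle and so does not cure the defect.

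The cost is a few sentences. No patient, visit or assessment changes. The downside is a less favourable stated objective.

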3.1 Patient Participants

3.1.1 Inclusion criteria

Patients will be included if they meet **all** of the following eligibility criteria:

1. Age ≥ 60 years on the day of surgery;
2. Scheduled major orthopedic surgery, or major surgical resection of a thoracic or abdominal malignancy, or major cardiac procedure;
3. Clinically significant depression or anxiety symptoms screened by the PHQ-ADS (Patient Health Questionnaire Anxiety and Depression Scale) ≥ 10 [7].

3.1.2 Exclusion criteria

Patients will be excluded from the study if they meet **any** of the following:

1. Estimated life expectancy < 12 months;
2. Unable to read, speak, and understand English;
3. Current alcohol or other substance abuse;
4. Severe cognitive impairment screened by the SBT (Short Blessed Test) ≥ 10 ;
5. Acutely suicidal (see instruments in Appendix A).

Data related to patient inclusion and exclusion will be gathered either via EHR chart review, and/or clinical PI discretion, and/or self-reported by patient during telephone screening process. Eligible patients will be offered the opportunity to participate in the study regardless of gender or minority status. Thus, the sample composition will reflect the composition of community-living older adults in the St. Louis area. All of our studies actively encourage the participation of minorities in the research.

3.2 Caregiver participants

Caregivers offer a unique perspective on a patient's mood and health status, and can be in a position to help effect change, engagement in activities and potentially our intervention bundle. Patient caregivers will be identified by the patient as a family member or friend who cares for the patient as needed to support health and safety, and often have additional care-related responsibilities in the perioperative period.

3.3 Participant Recruitment and Screening

We have outlined our multi-pronged approach to recruit patients, caregivers and clinicians for this study.

3.3.1 Patient recruitment

In all three cohorts, patients may be contacted by the study team and invited to screen if interested. Prospective patients will be identified by Epic workbench reports customized to limit results to those at least 60 years of age with an eligible surgery scheduled at BJH/WUSM. For the WUSM Orthopedic Surgery clinics, patients complete a PROMIS questionnaire as standard routine practice at appointment check-in. Given that the PROMIS scores are available for the orthopedic surgical patients, the EHR report will be further customized as needed based on PROMIS scores.

Initial contact by research coordinator may be made by phone, or in-person if the patient is on campus for a clinical visit in one of the collaborating departments. We will use an information sheet or phone script (see Appendix A) to introduce the goals of the center and the study. Additionally, recruitment flyers (see Appendix B) will be utilized to invite interested patients to contact the study team to screen. The IRB-approved flyers will be distributed to the waiting rooms and clinical offices of the clinicians seeing our target population, as well as the CPAP which many surgical patients visit prior to scheduled surgery. Lastly, patients can also be referred to the study by their clinician, either by offering a recruitment flyer to any patients who meet our inclusion criteria, or by the clinic team at the time of their clinic visit. Clinical teams may refer patients to the study team for screening, some by phone, or email to study team members, or email to [contact]. Some prospective participants may have clinic visits at the included Departments' satellite sites, and some orthopedic procedures scheduled through Washington University take place at Barnes-Jewish West County Hospital, where those patients may also be enrolled and have study visits. However, the majority of consenting and study procedures will take place within the WUSM and BJH Medical Center Campus.

3.3.2 Patient screening

We will then screen the patients who are interested to proceed in the study and provide a verbal consent. (Appendix A) The screening checklist (also in Appendix A) will be based on our eligibility criteria (see criteria above). To avoid burdening patients with the full PHQ-ADS at the time of screening, patients will first be asked to complete the brief PHQ-4 (i.e., first 4 questions of PHQ-ADS related to anxiety and depression) Patients who score ≥ 3 will continue with the remaining questions in the PHQ-ADS. Patients with a total score of PHQ-ADS ≥ 10 , and a SBT (Short Blessed Test) score of ≤ 9 will be invited to consent to participate in the study (Table 1). This will be completed at the time of recruitment by a trained member of the research team, and the screener can be collected by phone or in person per patient preference.

Table 1. Scored Instruments for Screening (see details in Appendix A)

Screening Instrument	Eligibility Criteria	Cut-off for Eligibility	Source
PHQ-4	Pre-screen Depr/Anx sx	Inclusion \geq 3	Self-report in screening instrument
PHQ-ADS	Clinically Significant Sx	Inclusion \geq 10	Self-report in screening instrument
SBT	Cognitive health	Exclusion \geq 10	Self-report in screening instrument

3.3.3 Caregiver recruitment

Patients may refer their caregivers (e.g., spouse, partner, children, friend) to contact the study team if interested, or if they prefer to share the caregiver's phone number, the study team contact them by phone and invite them. With the patients' consent, patients' caregivers are also invited to participate by phone, or mail. They will participate in a brief REDCap survey to report any changes related to confusion or delirium in the patient once *before* surgery, and once per week for 4 weeks *after* surgery (FAM-CAM attached). Additionally, some patients' caregivers (up to 25) will be invited to participate in a semi-structured interview (see Appendix J) after the patient's participation in the intervention has been completed.

3.4 Participant Consenting and Enrollment

3.4.1 Patient consent

Patients will be invited to read, discuss, review and ask any questions they may have about study participation with a study team member, and then complete the Informed Consent Form (Appendix C). The informed consent will be available either via a paper collected by mail or in person, or by secure REDCap link to e-consent, as per patient preference. Patients who meet all eligibility criteria in 3.1 and provide consent may be enrolled into the study per PI discretion. Some patients who meet the eligibility criteria but who may require additional clinical input before enrolling them into the study, will be discussed with the study team clinicians and the PI.

3.4.2 Caregiver consent

Caregivers will be invited to participate in semi-structured interviews about the intervention bundle that can be conducted via Zoom/Phone or in-person depending on participant convenience and choice. Hence, they will be consented verbally or with a written consent depending on their participation. If they consent to a semi-structured interview (Appendix J). The interviews with study patient caregivers, will provide valuable feedback on the intervention bundle. Caregivers may also consent verbally to participate in the FAM-CAM confusion and delirium assessment via phone, mail, or email link to REDCap survey.

4 Study Design

This is a feasibility study utilizing mixed methods. All eligible and consenting patients will receive the intervention bundle and will undergo a standard battery of assessments prior to the intervention and will be followed for approximately 3 months in the postoperative period. In conjunction with the

quantitative data collected, qualitative methods will be employed to evaluate acceptability, implementation and practicality of the intervention.

4.1 Assessments

At enrollment, a research coordinator will administer a battery of baseline assessments (see Appendix D) to characterize patient participants. Patient participants will complete these baseline assessments after consent:

- Demographics survey
- Medical History of Comorbidities
- Brief Pain survey
- BADS (Behavioral Activation Depression Scale)
- Brief survey of Patient Reported Falls past 3mo
- VR-12 Quality of Life survey
- SDM-4 (Shared Decision Making)
- PHQ-ADS (Patient Health Questionnaire Anxiety and Depression Scale, collected at screening in Appendix A)
- SBT (Short Blessed Test, collected at screening in Appendix A)
- Review of Medication list (at initial intervention visit) Ultra Brief Confusion Assessment Method (and 3D-CAM if UB-CAM is positive) or FAM-CAM, and/or delirium may be assessed by EHR review using the CHART-DEL [23] method (Appendix M).

Anxiety and depression assessment will use the PHQ-ADS, as described above. The use of this tool for this population is supported by a recent meta-analysis suggesting that the PHQ9 (on which this tool is based) has good sensitivity and specificity in the diagnosis of depression in older adults [9]. *Quality of Life* (QoL) will be assessed using the Veterans RAND 12 Item Health Survey (VR-12) [10]. The questions in this patient-reported survey correspond to the QoL domains of general health perceptions, physical functioning, role limitations due to physical and emotional problems, bodily pain, energy/fatigue levels, social functioning and mental health. *Cognitive function* assessment will be performed using the Short Blessed Test (SBT) as described above. The SBT is a reliable test for characterizing cognitive functioning in this setting [22]. *Falls* data will be collected by monthly Patient-Reported Falls Questionnaire, which will be collected by phone with other assessments or via a REDCap survey which can be emailed to participants one time per month asking about any falls over the last month.

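### The PHQ-ADS score that admits patients also appears to be the baseline for the single-arm effect size, so regression to the mean enters a figure meant to size later trials

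*Combined protocol and SAP*

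**What the plan says.** - **Entry.** Section 3.1.1 requires "Clinically significant depression or anxiety symptoms screened by the PHQ-ADS" at a total of 10 or more. Section 3.3.2 puts the PHQ-4, four items of the same scale, in front of it: "Patients who score ≥ 3 will continue with the remaining questions in the PHQ-ADS".
- **Baseline.** Section 4.1 lists the baseline battery and includes "PHQ-ADS (Patient Health Questionnaire Anxiety and Depression Scale, collected at screening in Appendix A". The SBT, also an eligibility test, has the same note. BADS and VR-12 do not. Table 3 places screening (Appendix A) at Time 0 and the baseline surveys (Appendix D) at Baseline/Time 1.
- **Design.** Section 4: "All eligible and consenting patients will receive the intervention bundle". There is no comparison arm.
- **Analysis.** Section 5 defines r = Z/√N from a Wilcoxon signed-rank test of each timepoint against baseline, with a 95% interval. It hypothesises improvement and intends the effect sizes for powering later trials.
- **Use.** Objective 2 is to "empirically test the effectiveness of our adapted perioperative mental health intervention bundle". The objectives paragraph adds: "Insights gained from this pilot study will inform the design of three clinical trials that are planned to start in Jan 2023".

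**The concern.** A PHQ-ADS score varies from one occasion to the next. Admitting patients because one reading was 10 or more selects some whose reading was unusually high that day. If that reading is also the comparator, the next score is expected to be lower on average even if the bundle does nothing. A control arm would show the same fall and cancel it, but this study has none. The planned 95% interval does not help, because it describes sampling error around whatever r estimates.

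The fall from selection has the sign that Section 5 hypothesises, so it can pass for benefit. At stake are the reading of objective 2 and the use of r for sizing. If the planned trials take r as a between-arm effect, they could be too small. Reach (primary) and completeness of the 1- and 3-month PHQ-ADS (secondary) do not depend on this.

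**Working it through.** **Which score is the baseline?** For the screening score: the note in 4.1 is attached only to PHQ-ADS and SBT, it points to the screening appendix, and no section describes a second PHQ-ADS before the intervention. For a fresh score: 4.1 introduces the battery as done after consent, and Section 11 has staff giving the PHQ-ADS at every assessment. Appendices A and D were not available to settle it. The first reading is the more natural one, but it is an inference.

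**Inputs from the documents.** Threshold 10; up to 45 patients; r = Z/√N; no control arm. The plan states no expected r, SD, retest correlation or power, so there is no figure of its own to reproduce. At N = 45, Z = 1.96 corresponds to r = 1.96/√45 = 0.29.

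**Assumed inputs.** Mean and SD of PHQ-ADS in those screened, retest correlation ρ, and scoring limited to 0–48. True change is zero and there is no time trend. The PHQ-4 step is not modelled; it selects in the same direction.

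**Model 1: stable true score plus independent normal error.** The expected fall is

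SD × (1 − ρ) × φ(a) / [1 − Φ(a)], with a = (9.5 − mean)/SD.

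For mean 10, SD 9, ρ = 0.7: a = −0.056, φ/(1 − Φ) ≈ 0.763, so the fall is 9 × 0.3 × 0.763 ≈ 2.06 points. Simulation with rounded, bounded scores gives 2.01 points, r = 0.30, and |Z| > 1.96 in 53% of samples of 45. Over means 6–12, SD 7 or 9 and ρ 0.5–0.85, the simulated fall is 0.6–4.4 points, r is 0.16–0.54, and |Z| > 1.96 in 18–99%.

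**Model 2: skewed scores** (negative-binomial, capped at 48, Gaussian copula, first score at least 10, N = 45). Selected settings:

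| Mean/SD in those screened | Latent retest correlation | Mean fall | r | Z > 1.96 toward improvement (nominal 2.5%) |
|---|---|---|---|---|
| 6/6 | 0.6 | 4.2 | 0.51 | 95–97% |
| 8/7 | 0.7 | 2.6 | 0.36–0.37 | 72% |
| 12/8 | 0.8 | 1.0 | 0.19 | 23% |
| 14/9 | 0.9 | 0.4 | 0.10–0.11 | 11% |

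Over the full grid (25 settings, observed retest correlation 0.56–0.89) the fall is about 0.4–4.2 points and r about 0.10–0.51. In the settings rerun with 36 or 30 patients, r is the same within 0.01.

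**What changes the size (model 2).**
- *Enriched recruitment.* Section 3.3.1 says of the orthopedic lists that "the EHR report will be further customized as needed based on PROMIS scores", without naming the domain. If recruitment draws the top 30–50% on a measure correlating 0.5–0.7 with PHQ-ADS, the fall becomes 0.2–3.8 points and r 0.02–0.46.
- *Time trends.* Baseline precedes major surgery and follow-up is 1 and 3 months after it. A uniform 2-point improvement unrelated to the bundle gives a fall of 2.4–6.1 points and r 0.41–0.65. A uniform 2-point worsening gives anything from a 2.2-point fall to a 1.6-point rise, with r −0.32 to 0.31.

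**Would a repeat baseline remove it?** With independent errors (model 1), yes: the change is −0.03 to 0.07 points and r −0.01 to 0.01. If screening and repeat share short-term fluctuation, only partly. In model 2, with a screening-to-repeat correlation of 0.80–0.95, 2.0–3.6 of the 4.2 points remain (6/6, 0.6) and 0.9–2.2 of the 2.6 (8/7, 0.7). For 12/8 at 0.8, with correlations of 0.85–0.95, 0.2–0.7 of the 1.0 remains. About none remains when screening correlates equally with the repeat and with follow-up.

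**The case against.** The strongest reply is that Appendix D may already repeat the PHQ-ADS. Section 4.1 has a coordinator give the battery at enrollment, after consent, and Section 4 promises assessments before the intervention. In that case the fault is an unclear label. This stands as a real doubt, but it does not clear Section 5, which never says which score is the baseline. A single-arm change also carries time effects under either reading.

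Second, this is a feasibility study, and PHQ-ADS change is listed as a potential outcome for a later RCT. That limits the weight. It does not remove the point, because objective 2 and Section 5 themselves give the pre-post effect size a role in testing effectiveness and in power. Section 5 does not say r will be the only sizing input, so the harm is possible rather than certain.

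Third, every magnitude is assumed. A low retest correlation over several months also absorbs real change in patients' state, so the selection component and natural recovery are not cleanly separable. That stands, and no central value is claimed.

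Fourth, a repeat adds burden and may remove little. Section 3.3.2 uses the PHQ-4 step "To avoid burdening patients with the full PHQ-ADS at the time of screening", and the interval between screening and baseline is not given. This also stands, and it is why the repeat is the lesser part of the fix.

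**Conclusion.** The concern holds, with medium confidence. On the natural reading of Section 4.1, the plan selects on a score and then measures change from that same score, without a control arm. The selection component is toward improvement in every no-trend setting examined. Its size cannot be fixed from the documents: about 0.4–4.2 points and r about 0.10–0.51 in the skewed-score model, and 0.6–4.4 points and r 0.16–0.54 in the normal-error model. Even the mildest skewed-score setting crosses Z = 1.96 toward improvement in 11% of null pilots, against a nominal 2.5%.

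The net direction of the observed change is not established, because recovery or surgery-related change may add to or offset the selection component. The conclusion is that r cannot be read as an effect of the bundle, and Section 5 should say so. This should be corrected before r is used for planning.

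**What to change.** 1. **Section 5 (needed under either reading).** State that the single-arm PHQ-ADS r includes regression to the mean and time effects such as natural recovery and surgery, that it does not estimate a between-arm effect, and that it will not by itself set the size of the planned RCTs. Cost: a few lines.
2. **Section 4.1 and Table 3.** Repeat the 16-item PHQ-ADS with the post-consent battery, before the first intervention session. Define that score as baseline in Section 5 and Tables 2 and 2.1, and keep the screening score for eligibility only. If Appendix D already repeats it, delete the note in 4.1 that ties it to screening. Cost: 16 items for up to 45 consented patients at an assessment already planned. The burden is real but does not fall on everyone screened.
3. **Section 5, if item 2 is adopted.** Report the screening-to-baseline change, which precedes any session, as a partial check on regression to the mean. It may show little if the interval is short. Cost: one line.

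If the repeat is judged too burdensome, item 1, together with a plain statement that the screening score is the baseline, still prevents the misreading. Item 2 without item 1 would not be enough.
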